#### PROTOCOL SYNOPSIS

Buprenorphine is a mu opiate partial agonist recently approved by the FDA as a pharmacotherapy for opiate dependence. Controlled clinical trials over the past ten years have provided overwhelming support for its therapeutic use. Suboxone, a sublingual combination tablet containing both buprenorphine and naloxone (an opiate antagonist) has been developed to mitigate abuse and diversion. It is anticipated that buprenorphine will attract a large number of patients with opioid dependence into treatment who are currently unwilling or unable to avail themselves of other pharmacological treatments. Buprenorphine treatment may either be long or short term, and many participants will desire to taper from buprenorphine after variable periods of treatment. Currently there is little systematically gathered information available to guide clinicians in the process of tapering patients from buprenorphine treatment. Experience with methadone suggests that tapering from buprenorphine may not be easy. It remains unclear whether the unique pharmacological profile of buprenorphine will make the process less onerous. This study will explore two strategies to discontinue buprenorphine treatment after a period of stabilization, comparing a relatively brief to a more gradual tapering schedule, taking into account the dose on which participants have been stabilized.

Specifically this study aims to compare, in the outpatient setting, the relative advantage of two taper schedules (7 vs. 28 days) of Suboxone (buprenorphine-naloxone) following four weeks of Suboxone stabilization. It is hypothesized that a more gradual taper schedule compared to a shorter one will result in lower rates of illicit opiate use (as reflected by urine toxicology tests) at the end of the taper. However, there may be an interaction between the rate of taper and the stabilization dose. The proportion of participants providing opiate free urines in each group will be compared at the end of the taper, as well as at other time points (i.e. at 1 and 3 months post taper). Safety, as reflected by Adverse Events (AEs) and Severe Adverse Events (SAEs), withdrawal severity, stabilization dose and treatment retention during the study will also be explored.

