## 2.0 Study Objectives

The primary objective of this clinical investigation is:

To compare, in the outpatient setting, the relative advantage of two rates (7 vs. 28 days) of Suboxone tapering following four weeks of flexible dose stabilization, as reflected by the proportion of participants providing opiate free urines at the end of the taper regimen. It is hypothesized that the longer tapering schedule will result in a higher proportion of participants giving opiate free urines on the day following the end of the taper, regardless of the stabilization dose.

Secondary objectives are:

- 1. To determine the effect of stabilization dose on the relative success of each taper schedule and
- 2. To determine the effect of treatment on:
  - a. Proportion of participants providing opiate free urines at 1 and 3 month follow-ups
  - b. Abstinence from other drugs of abuse at the end of the taper and at 1 and 3 month follow-ups;
  - c. Concomitant medication use for treating withdrawal symptoms, at the end of taper and at 1 and 3 month follow-ups;

Protocol # CTN-0003

Version 7C

- d. Signs and symptoms of withdrawal at the end of taper and at 1 and 3 month follow-ups;
- e. Level of craving for opiates at the end of the taper and at 1 and 3 month follow-ups; and,
- f. Participant satisfaction with the treatment at the end of the taper and at 1 and 3 month follow-ups.
- g. Number (#) and severity of AEs experienced by each group.

Analysis of the data assessing the secondary objectives in combination with the primary objectives will provide a comprehensive overview of the clinical utility of each tapering regimen.

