#### **9.2 Outcome Measures**

#### Primary Outcome Measure

In keeping with this hypothesis, there is one primary outcome, the proportion of participants providing opiate free urines in each group on the day following the end of the taper. This outcome will be evaluated at the end of the taper. It will also be evaluated at 1 and 3 months post completion of tapering.

Secondary Outcome Measure

Several secondary outcomes will be evaluated. These include:

- 1. Comparison of number of opiate free participants by stabilization dose and taper schedule.
- 2. Comparison of:
  - a. The number of opiate free urine specimens at follow-up
  - b. The number of all drug free urine specimens at follow-up
  - c. Frequency of concomitant medication used to treat withdrawal symptoms
  - d. Severity of withdrawal symptoms as assessed by COWS and ARSW
  - e. The mean VAS craving level of each group
  - f. The mean SQ score (participant satisfaction) of each group
  - g. The number and severity of adverse event

These measures will be analyzed within a time course framework. We will compute change from baseline to follow-up in measures taken only at those timepoints (ASI). For measures collected repeatedly throughout the taper schedule (COWS, ARSW, SQ, concomitant meds, adverse events), we will plot the pattern of responses by group over time.

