#### 9.4 Analysis Plan

Each of the primary and secondary outcome measures will be analyzed for the intent-to-treat population and for the evaluable participant population. Major differences in the results, if any, will be further explored. While there is every intention to be complete in describing the analyses to be performed, it is not possible to anticipate every contingency and some adjustments may be required to meet constraints posed by the structure of the data.

Equality of groups at baseline will be established by comparing demographic and drug use information collected on the ASI. A test of proportions will be used for main outcomes evaluated at treatment end. Continuous on-study data will be evaluated using three-factor analysis of covariance with detoxification schedule as one factor (fixed effect), stabilization dose as the second factor (fixed effect), and site as the third factor. Baseline demographic values, where they potentially affect the responses on study or where they are found to be unevenly distributed between groups at baseline despite randomization, may be investigated post hoc. Interaction effects including, but not necessarily limited to, taper schedule X dose, will be investigated post hoc. Repeated measures, survival, and time course analyses will be employed where appropriate.

Statistical tests will be two-sided at a 5% level of alpha. Confidence intervals will be two-sided with a 95% confidence coefficient.

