## 9.7 Post Hoc Analyses

During the course of conducting the primary and secondary analyses, the data may suggest other interesting differences in the treatment groups. Post hoc analyses are anticipated to explore these findings. One potential post hoc analysis would be the exploration of factors found to be significantly different between groups at baseline, as they relate to study outcomes. Another potential post hoc analysis would be the exploration of interaction effects in the Analysis of Covariance (ANCOVA) models of continuous data, including but not necessarily limited to, taper schedule X dose interactions. Still another possible post hoc analysis would be to look at the group differences based on intent-to-treat samples using randomization as the starting point of treatment. Analyses would then be conducted on data from 1 Month Post Randomization and at 3 Months Post Randomization (rather than post taper as in the primary analysis). This is made possible by the design, because participants in both groups are seen for equal contacts following randomization.

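### The taper-by-dose question is secondary objective 1, yet Protocol 9.4 and 9.7 label its interaction post hoc, and no interaction test is stated for the binary opiate-free outcome

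*Protocol*

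**What the plan says.** The question is posed in advance in several places. The Protocol Synopsis says: "However, there may be an interaction between the rate of taper and the stabilization dose". Section 2.0 gives as the first secondary objective "To determine the effect of stabilization dose on the relative success of each taper schedule". Section 9.2 lists as the first secondary outcome "Comparison of number of opiate free participants by stabilization dose and taper schedule". Sections 3.0 and 4.5 stratify randomization by the dose taken on day 0 (8, 16 or 24 mg), with a separate set of cards for each dose.

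The analysis text treats it differently. Section 9.4 says "Interaction effects including, but not necessarily limited to, taper schedule X dose, will be investigated post hoc". Section 9.7 lists, among potential post hoc analyses, "exploration of interaction effects in the Analysis of Covariance (ANCOVA) models of continuous data, including but not necessarily limited to, taper schedule X dose interactions". For the binary outcome, section 9.4 offers only this: "A test of proportions will be used for main outcomes evaluated at treatment end". Dose enters a model in one place, as a fixed factor in the three-factor analysis of covariance for continuous data, and no interaction term is listed there. The power statement in section 9.6 covers the overall taper comparison and the craving scale, not any comparison by dose.

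**The concern.** Asking how dose affects the relative success of two tapers is asking about effect modification, that is, a taper-by-dose interaction. Success in this trial is naturally the opiate-free urine, which is binary, and 9.2 confirms this by counting opiate-free participants. The protocol thus sets a planned secondary question and then gives post hoc status to the analysis that answers it.

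This is more than detail left to a statistical analysis plan. A plan that pre-specified the interaction would contradict 9.4, and a plan that followed 9.4 would leave the first secondary objective with no pre-specified interaction test. What is at stake is how far a finding about dose can be trusted. Dose-specific results will be noisy, and a post hoc label invites picking out the dose at which one taper appeared to work. Comparing the tapers separately within each dose does not show whether the taper effect differs between doses.

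**Working it through.** **The protocol's own power figure.** Inputs from section 9.6: 20% versus 32%, 240 per group, with 20% dropout as an alternative (240 × 0.8 = 192). Section 9.4 gives two-sided 5% tests.

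Power = Φ[(0.12 − c − 1.96·SE0)/SE1], where SE0 = √(2 × 0.26 × 0.74/n), SE1 = √((0.20×0.80 + 0.32×0.68)/n) = √(0.3776/n), and c is 0 without continuity correction or 1/n with it.

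| n per group | Uncorrected | Corrected | Stated |
|---|---|---|---|
| 240 | 85.2% | 82.7% | about 82% |
| 192 | 76.6% | 72.9% | 72% |

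The stated figures match the continuity-corrected calculation. They apply to the overall comparison only.

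**Within one dose.** The protocol gives no dose split, so equal thirds is an assumption: 240/3 = 80 per arm per dose.
- SE1 = √(0.3776/80) = 0.0687, so the 95% CI half-width is 1.96 × 0.0687 = 0.135, or 13.5 points, against a target effect of 12 points.
- SE0 = √(2 × 0.1924/80) = 0.0694.
- Power without correction: Φ[(0.12 − 0.1359)/0.0687] = Φ(−0.23) = 41%.
- Power with correction: Φ[(0.12 − 0.0125 − 0.1359)/0.0687] = Φ(−0.41) = 34%.

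**Unequal strata.** Section 4.5 expects the numbers on each dose to vary. If the split were 10/30/60% (illustrative), there would be 24, 72 and 144 per arm. The half-widths 1.96·√(0.3776/n) are then 24.6, 14.2 and 10.0 points.

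**Difference in taper effect between two doses, 80 per arm each.** SE = √(2 × 0.3776/80) = 0.0972. Power for a 12-point difference is Φ(0.12/0.0972 − 1.96) = Φ(−0.73) = 23%. A difference of (1.96 + 0.84) × 0.0972 = 27 points is needed for 80% power.

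**2-df interaction test across three doses.** Assumptions: 20% on the 7-day taper at every dose, a simple average taper effect of 12 points, and 80 per arm per dose. With dose-specific differences d_i, weights w_i = 1/var(d_i) and weighted mean m, the noncentrality is λ = Σ w_i(d_i − m)².
- Effects of 0, 12 and 24 points: variances 0.00400, 0.00472 and 0.00508; m = 0.110; λ = 6.37; power 61% (47% on the logit scale).
- Effects of 6, 12 and 18 points: variances 0.00441, 0.00472 and 0.00495; m = 0.118; λ = 1.54; power 18% (14% on the logit scale).
- With the 10/30/60% split, the 24-point spread has power between about 31% and 45%, depending on scale and on which dose has the larger effect.

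**The case against.** Several counterarguments have force.

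- A reader might infer that the plan restricts the interaction to continuous data throughout. It does not. The sentence in 9.4 has no such limit, although it follows the description of the analysis of covariance. Only 9.7 mentions continuous data, and there as one potential example.
- A reader might infer that objective 1 has no planned analysis at all. That is too strong. Section 9.2 lists a comparison by dose and taper on the binary outcome, and 9.4 commits to analysing every secondary outcome. What is missing is a stated test of whether the taper effect differs by dose.
- A reader might infer that the hypothesis, worded to hold whatever the stabilization dose, can be examined only through a post hoc analysis. It can equally mean an effect pooled over doses, which the primary test addresses.
- The synopsis lists stabilization dose among the items to be explored, and low power fits exploratory status. This supports modest claims. It does not reconcile a numbered secondary objective with a post hoc label.
- Choosing between a logistic term and a homogeneity test is commonly left to the analysis plan. That is true, but the post hoc label stands in the protocol and has to be corrected there.
- Counting opiate-free participants, as 9.2 does, might be thought to bias the taper comparison. Within a dose, 1:1 stratified allocation keeps the arms near equal, so it does not. Only comparisons across doses would suffer, which makes this a wording point.

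**Conclusion.** The inconsistency is real and of moderate weight. The protocol plans the taper-by-dose question and stratifies for it, then labels the interaction post hoc and states no interaction test for the binary outcome. The primary analysis is untouched, and the point does not depend on any number.

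The figures show what a corrected plan can deliver. Under equal strata, an assumption, each dose-specific difference carries about ±13.5 points, with 41% power for 20% versus 32% (34% with continuity correction). A 2-df test has power below 20% for a modest spread of effects. Unequal strata make the smaller strata less precise. A non-significant interaction would therefore not show that the taper effect is the same at every dose. Because the physician chooses the dose, the trial can support statements about effect modification but not about the effect of dose itself.

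**What to change.** - In 9.4 and 9.7, remove the post hoc label for taper-by-dose. Other interactions may keep it.
- Pre-specify, as a secondary analysis, a 2-df taper-by-dose test on the end-of-taper opiate-free outcome, using the dose strata from randomization. This can be a new secondary logistic model or a test of homogeneity of risk differences across dose strata. The protocol has no logistic model at present, so this is an addition. The primary test of proportions stays as it is.
- Report the proportion opiate-free by taper and dose, with dose-specific risk differences and 95% confidence intervals. Put the same interaction term in the secondary analyses of covariance.
- State that power for these comparisons is limited, that a non-significant interaction is not evidence of a uniform effect, and that only effect modification will be claimed.
- Minor: in the first secondary outcome of 9.2, write proportion in place of number.

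The cost is one extra secondary model and an open statement of low power. It needs no extra participants, visits or data. If the sponsor prefers not to pre-specify the test, recasting objective 1 as exploratory would at least remove the contradiction, at the price of a weaker answer.

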## 9.5 Descriptive Statistics

Summaries of the characteristics of the participant population in both treatment arms at baseline will be prepared to investigate group equality at baseline as well as provide information necessary for decisions about covariates in post hoc analyses. A summary will be prepared to show dropouts/retention over time in each treatment group. The number of missing observations will be compared between treatments. The compliance of each group at each assessment day will be summarized.

Treatment effects will be summarized by gender, ethnicity, and age group separately. No attempt will be made to assess these factors together in order to maintain power for the main comparisons.

All adverse events will be reported in tabular form indicating the frequency of each type of event by various demographic characteristics such as gender, ethnicity, age, duration of addiction, other medical problems both related to and independent of the addiction.

## 9.6 Sample Size Estimate

The sample size determination was based on how many opiate users seeking treatment that the sites are capable of recruiting. With 11 sites, each site would be responsible for randomizing approximately 44 participants. It is possible that recruitment may not be

Protocol # CTN-0003

Version 7C

Date of Preparation: 1/31/05

Page 37 of 44

adequate at some sites and therefore enrollment may not be equal across sites. The total N will remain at 480

In a Phase III study for evaluation of the efficacy and safety of the combination product of buprenorphine and naloxone in opiate dependence, Study 1008, the percent of participants with opiate free urine samples after four weeks of treatment was 5.8% in the placebo group, 21% in the buprenorphine group and 18% in the combination group. Assuming that the percent of opiate free urine samples in a control group is 20%, the difference of 12% is considered a clinically significant improvement, and 240 participants per group would provide approximately 82% power for detecting this 12% difference. If 20% of participants dropout in the current study, and dropout occurs at random, then the sample size of 240 participants per group will provide 72% power for detecting a difference of 12%.

In Study 1008A, the mean craving score at Week 4 was 55.1 in the placebo group, 29.8 in the monotherapy group and 33.0 in the combination group. The standard deviation of VAS was estimated from the confidence interval for the difference between treatment groups presented in the 1008 study report. It was estimated to be 40.7. The sample size of 240 per group will provide at least 90% power to detect a difference between the mean craving scores of 33 and 44 at the 0.05 level.

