## 3.0 Study Design

This is a randomized, parallel-group, open-label study. After screening and baseline assessments, participants will receive a three-day Suboxone induction and a 25 day stabilization, (total 28 day stabilization phase). For three weeks (days -28 to -8) the dosing is flexible, but in the final week of the stabilization phase (days -7 to -1 and randomization day 0), participants must be on a stable dose of either 8mg, 16mg, or 24mg of buprenorphine. On day 0 participants will be randomly assigned in a 1:1 ratio to one of two Suboxone tapering regimens. If, for some reason, the participant is unable to attend on day 0, there will be a 3 day window for randomization to occur. Regardless of the actual day on which randomization occurs, it will be named as day 0 (it may occur up to, but no longer than, three days after the actual day 0). Randomization will be stratified, within site, according to the dose being taken on day 0 (8, 16 or 24 mg of buprenorphine). Tapering regimen #1 will be performed over 7 days and regimen #2 will be performed over 28 days. Participants in both groups will be seen weekly for data collection through day 56, followed by a 3 month post randomization visit on Day 84 for both groups and a 3 month post taper follow-up on days 91 and 112 respectively. This design will allow the investigators to analyze the data in either a post taper or a post randomization design. All participants will participate in an equal number of data collection visits throughout the study. Data will be available for 1 and 3 Months Post Taper, as well as 1 and 3 Months Post Randomization.

The maximum length of study participation is expected to be approximately 5 months, including screening, stabilization, tapering, post-tapering and follow-up. All participants will also participate in TAU from the time of consent through at least the end of the taper, at the CTP that manages their study participation. Following the taper, participants may continue in TAU at the CTP or be referred to other available local resources.

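### The craving power of at least 90% in Section 9.6 is about 84% under the protocol's own inputs and two-sided 5% test

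*Protocol*

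**What the plan says.** Protocol Section 9.6 (Sample Size Estimate) takes a standard deviation for the craving visual analogue scale from an earlier study: "It was estimated to be 40.7". It then claims that "240 per group will provide at least 90% power to detect a difference between the mean craving scores of 33 and 44". The sentence sets the significance level to 0.05 but does not say whether the test is one- or two-sided.

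Section 9.4 (Analysis Plan) settles this for the whole trial: "Statistical tests will be two-sided at a 5% level of alpha". It makes no exception for secondary outcomes. Section 3.0 fixes 1:1 allocation.

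For the urine outcome, Section 9.6 gives about 82% power for a 12-point difference from a 20% control rate. It lowers this to 72% for the scenario introduced by "If 20% of participants dropout in the current study, and dropout occurs at random". It gives no such reduced figure for craving.

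**The concern.** All inputs to the craving calculation are in the document, and together with the two-sided rule they do not give 90%. The claim is worded as a minimum, so rounding cannot explain a shortfall.

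Craving is a listed secondary objective (Section 2.0) and outcome (Section 9.2), and it is the only secondary outcome with a stated power. A reader of a null craving result would take it that an 11-point difference had at most a 10% chance of being missed. The figure also makes the trial look clearly better powered for craving (at least 90%) than for its primary outcome (about 82%), when the two are nearly equal.

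**Working it through.** **Inputs**

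| Quantity | Value | Source |
|---|---|---|
| Difference in means | 44 − 33 = 11 | 9.6 |
| Standard deviation | 40.7 | 9.6 |
| Participants per group | 240, allocated 1:1 | 9.6, 3.0 |
| Significance level | 0.05 | 9.6 |
| Sidedness | two-sided | 9.4 |
| Dropout scenario | 20% at random, 240 × 0.80 = 192 per group | 9.6, stated for the urine outcome |

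**Step 1. Standardised difference at 240 per group**

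SE = SD × √(2/n) = 40.7 × √(2/240) = 3.715

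11 / 3.715 = 2.961

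**Step 2. Attempt to reproduce the stated 90%**

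- Two-sided 0.05: Φ(2.961 − 1.960) = Φ(1.001) = 0.842 (noncentral t: 0.840). Not reproduced.
- One-sided 0.05: Φ(2.961 − 1.645) = Φ(1.316) = 0.906 (noncentral t: 0.905). This matches the stated figure.
- Two-sided Wilcoxon test at 95.5% relative efficiency: 0.825. Not reproduced.

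Of the variants tried, only the one-sided test reaches 90%.

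**Step 3. Which convention does the rest of Section 9.6 use?**

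The urine powers were recomputed for 20% versus 32%, using a pooled test of proportions with continuity correction:

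| Per group | Two-sided | One-sided | Protocol states |
|---|---|---|---|
| 240 | 82.7% | 89.6% | about 82% |
| 192 | 72.9% | 82.3% | 72% |

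The urine figures are two-sided. The craving figure therefore departs both from Section 9.4 and from the other calculation in its own section.

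**Step 4. Craving under the 20% dropout scenario**

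SE = 40.7 × √(2/192) = 4.154

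11 / 4.154 = 2.648

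Two-sided power: Φ(2.648 − 1.960) = 0.754 (noncentral t: 0.752)

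**Step 5. What 90% two-sided power would require**

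- Detectable difference at 240 per group: (1.960 + 1.282) × 3.715 = 12.04 points (12.07 with the t distribution).
- Detectable difference at 192 per group: (1.960 + 1.282) × 4.154 = 13.5 points.
- Per-group size for 11 points: 2 × 40.7² × (1.960 + 1.282)² / 11² ≈ 288 (289 with the t distribution).
- Standard deviation at which 240 per group suffices for 11 points: 11 / [(1.960 + 1.282) × √(2/240)] ≈ 37.2.

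**The case against.** The arithmetic is not in dispute. The case on the other side concerns its weight and some of the surrounding claims.

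- **The figure drives nothing.** Section 9.6 says the sample size follows from recruitment capacity and stays at 480. Craving is secondary, and the corrected 84% is still slightly above the power accepted for the primary outcome. This stands: the error misstates what the trial can show on craving, but it does not alter the design or the primary analysis.
- **The 75% corrects no stated figure.** The protocol gives dropout as a conditional scenario and applies it only to the urine outcome. This also stands: 75% is that scenario carried over, and it should be labelled so. The 84% does not depend on it.
- **The sidedness is inferred.** The craving sentence says only that the level is 0.05. But Section 9.4 covers all tests without exception, and the urine powers are two-sided. If a one-sided test was meant, Sections 9.4 and 9.6 contradict each other, so a correction is needed on either reading. That a one-sided calculation was the cause remains a likely explanation, not a documented one.
- **The planned analysis might do better.** Section 9.4 plans an analysis of covariance with schedule, dose and site, and repeated-measures analyses where suitable. These could raise power, but no baseline craving covariate is named and Section 9.6 assumes no reduction in variance. The 90% cannot be credited to them.
- **Over-reading of a null result is not certain.** No claim of equivalence is planned for craving, and Section 9.4 provides 95% confidence intervals that would show the imprecision. This limits the harm but does not make the stated power correct.

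**Conclusion.** The stated power is wrong as written. For an unadjusted two-group comparison with standard deviation 40.7, a difference of 11, 240 per group and a two-sided 5% test, power is 84%, not at least 90%. The type II error is about 16%. If 20% drop out at random, as in the section's urine scenario, power is about 75% and the type II error about 25%.

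The result takes the protocol's standard deviation as given and reads the craving sentence under the two-sided rule of Section 9.4. The error is confined to this secondary outcome.

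**What to change.** Replace the craving power sentence in Section 9.6 with a statement along these lines:

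> With 240 per group and a standard deviation of 40.7, a two-sided 5% test has 84% power for mean craving scores of 33 versus 44. If 20% of participants drop out at random (192 per group), power is about 75%. The difference detectable with 90% power is about 12 points at 240 per group and 13.5 points at 192 per group.

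Keep the total at 480. Reaching 90% power for 11 points would take about 289 evaluable participants per group, which a secondary outcome does not call for.

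Optionally, if the Day 0 craving score is to be a covariate, power may be quoted on that basis, provided the assumed correlation with the outcome is stated. The standard deviation must fall to about 37.2, so the correlation needed for 90% before dropout is √(1 − (37.2/40.7)²) ≈ 0.41. The protocol gives no such value at present.

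The cost is a short rewording in one section and a less favourable power figure. No participants, visits or analyses are added.
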